Official Title: Oxygen Reserve Index Validation
for RD Lite Sensors

Date of Protocol: August 1, 2017

NCT Number: NCT03128892

Protocol/Test Procedure Title	Oxygen Reserve Index (ORI)
Lead Investigator	[name], MS, BS Clinical Lab Manager Masimo Corporation [name]
Other Investigators	[REDACTED] Assistant Clinical lab Manager Masimo Corporation [name] [REDACTED] Clinical Research Associate Masimo Corporation [name]
Expected Start Date	Based on IRB Approval Certification Approval Date
Expected End Date	Based on IRB Approval Certification Expiration Date
IRB	E&I West Coast Board – IRB00007807
Date Submitted To IRB	

Protocol Test Abstract:

This document describes a procedure to collect optical and invasive reference data for the development of Masimo's devices and sensors. Non-invasive data from devices and blood levels of oxygen reserve index (ORI) as well as other non-infectious blood solutes will be measured during [REDACTED] [REDACTED] conditions in order to evaluate and calibrate the system. This protocol may involve optical data collection, placement of arterial and venous line(s), and intermittent blood sampling for reference machines.

APPROVALS

Author	Date	Engineering	Date
Quality Assurance	Date	Manufacturing	Date

This document is a protocol for a clinical research study sponsored by Masimo Corporation. The study will be conducted in compliance with all stipulations of this protocol, the conditions of IRB approval, the Declaration of Helsinki, ISO-14155, applicable regulatory requirements and International Conference on Harmonization Good Clinical Practice guidelines ICH GCP.

1. PURPOSE

The primary objective of this study is to collect data using noninvasive devices from healthy volunteers undergoing a desaturation procedure.

Devices to be used in this study will use Masimo SET technology and Masimo Rainbow technology sensors. Devices and sensors may be FDA-cleared or investigational.

All investigational devices and sensors undergo a risk assessment evaluation prior to use on human subjects to safeguard subjects. No device or sensor that fall under a significant risk device classification as defined in 21 CFR 812.3(m) and determined by the IRB will be used under this protocol.

[REDACTED] . Pulse oximeters or similar non-invasive devices that are FDA approved or that are investigational may also be tested during this study if needed.

2. BACKGROUND

Masimo Corporation develops non-invasive medical technologies. These devices have applications in the operating room, critical care unit, emergency room, emergency transport vehicles, as well as physician's offices.

[figure not shown]
A blood sample gives the best measure of hemoglobin as well as other blood solutes but is difficult to measure continuously and without skin puncture and risk of infection. Masimo SET and Masimo Rainbow technology allows real-time, non-invasive monitoring of hemoglobin (and other blood

solutes) in patients and has the potential to improve clinical outcomes while reducing the cost of care and risks to both patients and clinicians associated with venipuncture.

2.1 TECHNOLOGY BACKGROUND

Pulse oximetry is governed by the following principles:

1. Oxyhemoglobin (oxygenated blood) and deoxyhemoglobin (non-oxygenated blood) differ in their absorption of red and infrared light (spectrophotometry).
2. The amount of arterial blood in tissue changes with arterial pulses (photoplethysmography). Therefore, the amount of light absorbed by the varying quantities of arterial blood changes as well.
3. More generally, Masimo Pulse CO-Oximeters use a multi-wavelength sensor to distinguish between not only oxygenated blood and deoxygenated blood, but also blood with carbon monoxide, oxidized blood and blood plasma. The CO-Oximeter utilizes a sensor with various light-emitting diodes (LEDs) that pass light through the site to a photodiode (detector). See figure below.

1. Light Emitting Diodes (LEDs)
(2+ wavelengths)
2. Detector

4. Signal data is obtained by passing various visible and infrared lights through a capillary bed (for example, a fingertip, a hand, a foot) and measuring changes in light absorption during the blood pulsatile cycle. The detector receives the light, converts it into an electronic signal and sends it to the Rad-57, or similar Masimo hardware platform, for calculation.
5. Once the oximeter receives the signal from the sensor, it utilizes Masimo SET signal extraction technology for calculation of the patient's functional oxygen saturation and pulse rate, total hemoglobin, and/or other physiological parameters.

2.2 STUDY DEVICES

Devices used in this study may be either:

- Masimo FDA cleared devices used according to the FDA-approved indication, or
- Masimo investigational devices, which:
 - Are FDA-cleared devices used outside the FDA approved indication, or
 - Are novel prototypes or modified versions of the FDA-cleared products (with or without minor hardware and software adjustments) that do not pose increased risks to subjects.
 - Are non-significant risk devices.
 - Undergo a risk assessment evaluation prior to use in human subjects to safeguard subject safety.

2.2.1 Current Masimo Predicate Devices

Masimo rainbow SET® is a noninvasive monitoring platform featuring Masimo SET® Measure-through Motion and Low Perfusion™ pulse oximetry with the option to measure multiple additional blood constituents and physiologic parameters. Masimo rainbow and SET technology describes a line of sensors that all use the same pulse oximetry type technological concepts to read physiological parameters. Conventional pulse oximetry uses two LED (light emitting diodes) to emit light through one side of the finger and a detector on the other side that reads the amount of light that makes it through the digit. With rainbow technology Masimo uses additional wavelength LEDs in order to calculate more complex blood solute concentrations like hemoglobin concentration. The same principles described above that govern Masimo SET technology (pulse oximetry) also govern Masimo Rainbow technology. These additional LEDs do not present any additional risk to the end user since they radiate light in the same wavelength and power ranges.

Depending on the number and type of LED Emitters, the investigational device can provide non-invasive estimates of a number of physiological parameters. See Table 1.

Oxygen Saturation (SpO ₂)	Pleth Variability Index (PVI®)
Pulse Rate (PR)	Methemoglobin (SpMet®)
Perfusion Index (PI)	Carboxyhemoglobin (SpCO®)
Total Hemoglobin (SpHb®)	Acoustic Respiration Rate (RRa®)*
Oxygen Content (SpOC™)	

Table 1. List of currently FDA cleared Masimo non-invasive technology.

2.2.2 Masimo Rainbow Pulse CO-Oximeter and Other Non-Invasive Sensors

The Masimo Rainbow SET CO-Oximeter platform is FDA 510(k) cleared for the noninvasive and continuous monitoring of total hemoglobin concentration in adults. The devices under test may be investigational versions of the Masimo [REDACTED] approved pulse oximeters, sensors or other monitoring devices.

Investigational devices are modifications of FDA-cleared products. They may differ from FDA-cleared products [REDACTED]. Each aspect of the investigational device's modification is considered for impact on subject safety, and all investigational devices undergo a risk analysis assessment to identify required safety tests or risk mitigation strategies prior to use on any study subject. [REDACTED]

[REDACTED]

[REDACTED]

[REDACTED]

[REDACTED]

[REDACTED]

5. EQUIPMENT, MATERIALS AND SAMPLE SIZE JUSTIFICATION

5.1. Safety equipment and Blood Analyzers Maintenance:

- 5.1.1. All blood analyzers, ECG monitors, Blood pressure monitors and safety equipment will be maintained per manufacturer specifications and all study personnel will be trained on the use of relevant equipment.
- 5.1.2. The blood pressure cuff, ECG monitors, and FDA cleared oximeter will be used for monitoring of the participants for their safety.
- 5.1.3. The blood analyzers will be used to run blood samples collected throughout these studies for analyzing blood solutes that are relevant to specific noninvasive technology readings being tested. e.g. Blood will be run for purposes of reading hemoglobin from sample compared to non-invasive hemoglobin reading from Masimo Hemoglobin sensor.

5.2. Equipment and Materials: to be used as required

Standard safety monitors will be used for this study
(e.g. ECG, FDA-cleared pulse oximeter, BP cuff)

Equivalent equipment and materials to those listed below may be used: All lab analyzers and equipment will be maintained per manufacturer specifications and all study personnel will be trained on the use of relevant equipment.

Subject safety monitoring equipment and medical supplies

- Non-invasive blood pressure arm cuff(s)
- ECG monitor – FDA approved product
- Urine HCG pregnancy test -female subjects only
- Standard band aids, needles, syringes, sharps container or other standard medical, wound care equipment and biohazard waste containers necessary to carry out the test procedure
- Standard Emergency equipment and medications will be available in on-site during the study
- 0.5%-2% lidocaine
- Ethyl Chloride/Pain Ease
- Heparin or saline flush solution (as required)- or equivalent
- Arterial blood pressure transducer

FDA-Cleared devices and sensors

- Rainbow Sensors
- Conventional Pulse Oximeters
- Conventional Pulse Oximeter Sensors

Investigational devices and sensors

- Pulse Oximeters
- Pulse Oximeter Sensors
- Pulse Oximeter Patient Cables

Oxygen administration equipment

- Medical grade O₂
- Oxygen mask
- Mouthpiece
- Nasal Cannula

Desaturation equipment and safety equipment

- Gas tanks, regulators

General lab supplies
[REDACTED]

- Stopwatch
[REDACTED]

5.3. Sample size justification
[REDACTED]

5.4. Standard Precautions

- 5.4.1. Subjects will have continuous ECG monitoring throughout the study (may not be recorded/ for monitoring by medical staff).
- 5.4.2. ACLS certified physician will be in attendance (in the study space) throughout the entire procedure, and the study will be completed under their general supervision.
- 5.4.3. Any emergency drug deliveries in the case that a subject loses consciousness or has another emergency arise (standard crash cart medications- atropine, ephedrine etc.) shall be recorded. This individual will be monitored and this information will be recorded and submitted to the IRB if necessary (unanticipated adverse event) and the subject will be given the option to follow up with a local urgent care facility.
- 5.4.4. The volunteer will be monitored (through observation by clinical study staff) throughout the study procedure.
 - 5.4.4.1. An additional pulse oximeter will occasionally be used for the duration of the study to monitor subjects' vital parameters to ensure their safety.
- 5.4.5. All adverse events will be recorded.

6. PROCEDURE

Overview: During this study we will recruit human subjects; this will include members of the general public and Masimo employees, to participate in a study. [REDACTED]

[REDACTED] During this study we will be testing the sensors in order to make a desaturation assessment of our noninvasive devices (listed above). Participants in this study will come in and be seated, review the consent information, agree or not. One or more clinician(s) will place [REDACTED] and arterial line(s), and sensors will be placed. The clinician will collect [REDACTED] blood samples which will be run on our internal blood analysis equipment ([REDACTED]). This blood sampling will serve the purposes of a comparison tool for the readings that were recorded from the noninvasive devices and sensors.

Pulse oximetry monitoring will take place throughout the study. During this study subjects [REDACTED]: continuous reference blood sampling [REDACTED] and oxygen administration. [REDACTED]

6.1 RECRUITMENT

6.1.1 Advertisement

Recruitment materials are posted publically in local newspapers, Craigslist, schools/universities etc.

6.1.2 Phone Screening

Potential subjects can contact Masimo to inquire more details about the study. The recruitment process is managed by the designated person(s) who is trained for phone screening/scheduling. Appointments are made once the phone screening process is completed and the person screening the subject determines if they qualify or not for the study based on inclusion and exclusion criteria.

**6.2 PRE-ENROLLMENT SCREENING AND EXAM**

- 6.2.1 Subjects will be asked to provide a copy of their valid government photo ID and/or Social Security (SSN) to verify subject information in our scheduling database and/or to verify the subjects' identity. Foreign persons (A foreign person includes a nonresident alien individual and certain foreign entities that are not U.S. persons) will be asked to provide a copy of U.S. immigration documents/Tax ID Number (TIN) or equivalent, and to complete a W-8BEN form to report earnings to the Internal Revenue Service (IRS).

The copies of these forms of identification will be stored along with the subjects consent documents. The confidentiality and retention of these documents will be protected to the extent provided and required by the law.

The SSN number and ID card is kept to verify subject's identities or instances to track subjects who provide false identification.
- 6.2.2 Subjects will be informed of the procedure prior to participating in the study. Subjects must read and sign the consent document, using our informed consent process. The consent form must be stamped with a current IRB approval. No study related activities will be conducted until consent is signed.
- 6.2.3 Weight is self-reported by the subject, but if the subject appears to be outside the weight range based on the inclusion/exclusion criteria, subjects will be weighed on a scale.
- 6.2.4 After consenting, subjects will be asked a brief series of health questions to ensure their eligibility for this study. Subjects who do not meet the inclusion and exclusion criteria will not be eligible to participate in the study.
- 6.2.5 Subject demographic information including age, sex, skin tone, ethnicity, height and weight will be collected.
- 6.2.6 In addition, a medical history will be recorded after initial screening questionnaire. Pre-procedural vital signs will be recorded for subject safety monitoring.
- 6.2.7 Female subjects will be required to take a pregnancy test. Results will be noted. If the pregnancy test is positive the subject will be removed from the study and notified of their pregnancy test results.

6.2.8 A venous blood sample will be obtained and analyzed [REDACTED]

6.2.9 Blood samples will be discarded after testing. These samples will be discarded in the appropriate biohazard waste bins and the samples are de-identified

6.2.10 Subjects may have a blanket placed on them (per request of subject or staff).

6.2.11 Subjects may be offered a snack (ie. Granola bar) and/or beverage (ie. Water, juice) due to the amount of time their involvement in this study may take.

6.3.5 Upon successful placement of the [REDACTED], Arterial line and the volunteers' indication that they are comfortable, optical sensors for noninvasive measurement(s) will be placed on the subjects fingers.

[REDACTED]

[REDACTED]

[REDACTED]

6.4 ORI PROCEDURE

6.4.1 Upon successful placement of the safety monitors and the volunteer's indication that they are comfortable, a baseline set of blood samples will be obtained.

[REDACTED]

[REDACTED]

[REDACTED]

[REDACTED]

A qualified person will complete blood draws.

6.4.5 Subjects will be given supplemental oxygen through a nasal cannula, mouth piece or mask during some portion of the study. This is to simulate the high oxygen environments [REDACTED] and test our sensors performance during oxygen administration.

[REDACTED]

[REDACTED]

[REDACTED]

[REDACTED]

6.4.7 The process will be stopped if there is any evidence of volunteer stress or distress.

[REDACTED]

[REDACTED]

[REDACTED]

6.4.9 Any blood not used for analysis will be discarded.

6.5**DESATURATION PROCEDURE**

Subjects may also be taken to different saturation levels below room air.

6.5.1 Other standard output parameters may also be recorded from the device(s) (SpO₂, SpMet, SpCO, PVI, PI, pulse rate are some examples of these).

6.5.2 Note: There will be a medical grade oxygen tank next to the subject, equipped with an oxygen mask, ready for a scenario where a subject needs 100% oxygen immediately. At any point in the study, if the subject feels uncomfortable, the subject will be given 100% oxygen. The subject's mouthpiece and nose clip will be removed and oxygen will be administered until medical personnel determine the subject is asymptomatic and the subject acknowledges they are feeling better.

6.6**ENDING PROCEDURE**

6.6.1 The total time will be approximately

6.6.2 At the conclusion of the procedure, the sensors/devices [REDACTED] and the arterial line(s) will be removed and the volunteer will be allowed to leave after medical personnel determine it is safe to do so.

6.6.3 All volunteers will be encouraged to remain in the study area until they feel fit to leave; subjects should feel safe and able before returning to work directly after participation in the study. All subjects including subjects that are employees of Masimo will be advised to take as much time as they need after the study before returning to work.

6.6.4 Volunteers will be given instructions on wound care. All volunteers will be instructed to contact the principal investigator and/or study staff in the event of any potential complication.

6.6.5 Volunteers will be paid according to the compensation breakdown on the consent form.

6.6.6 Subjects will be provided with information related to any significant new findings that develop at any time during the study which may relate to their willingness to continue their participation, their health and/or medical care.

6.7**TIMING REQUIREMENTS FOR SUBJECT PARTICIPATION**

[REDACTED]	[REDACTED]

7. ACCEPTANCE CRITERIA (IF APPLICABLE)

[REDACTED]

8. DATA ANALYSIS PROCEDURE TO BE USED

[REDACTED]

8.2. Sample size and level of significance and power

[REDACTED]

8.2.1. Study variables

[REDACTED]

8.2.1.1. Devices (see section 2 for descriptions and limits)

8.2.1.2. Procedures (see section 6 for descriptions and limits)

- 8.2.1.3. Subjects (see section 9 for descriptions and limits)
- 8.2.1.4. Other: None allowed unless named.
- 8.2.2. Measures taken to minimize/avoid bias:
 - 8.2.2.1. Subjects are selected from the population surrounding the test site (including employees). Where applicable, subjects with required demographics (skin color, age, gender, etc.) may be preferentially recruited.
 - 8.2.2.2. Sensors and devices will be provided to operators in a way that [REDACTED]
[REDACTED]
 - 8.2.2.3. Operators will not make any decisions based on results from other operators or any parameters obtained from blood samples.
- 8.3. Statistical Design
 - [REDACTED]
[REDACTED]
 - 8.3.2. When applicable, [REDACTED]
[REDACTED] describe any reasons for terminating the study early.
[REDACTED]
[REDACTED]
- 8.4. Data Quality Assurance
 - 8.4.1. The investigator/study staff shall prepare and maintain accurate case histories designed to record all observations and other data pertinent to the study for each study participant. All information shall be recorded on the case report forms.
- 8.5. Case Report Forms
 - 8.5.1. Data shall be entered into a Case Report Form. The relevant data on the Case Report Forms will be transferred into a database for analysis. No subject identifiers will be collected on the Case Report form. Access to the completed Case Report Forms will be locked and the Study Database will be password protected, both limited to study personnel.
 - 8.5.2. Case report forms will capture protocol deviations and will prompt any notifications to the IRB.
- 8.6. Expected Dropout Rates

There are two possible dropout causes:

8.6.1. The first is if the sensor/device fails to provide a valid reading on a Subject. Depending on desired endpoints and parameter statistics, [REDACTED] may address how many valid measurements are required to include a subject in the analysis. The second is if the Subject does not wish to complete the study. All subjects have the right to terminate the study at any time. Depending on the number of valid measurements taken prior to termination, the sponsor may elect to keep the collected data.

[REDACTED]

[REDACTED]

9. SUBJECTS

Potential subjects may be recruited and enrolled according to the criteria below.

[REDACTED]

[REDACTED]

Inclusion Criteria (Eligible Subjects)

- Competent non-smoking (smokers including e-cigarette users) adults between the ages of 18 and 50 years of age.
 - We may also be interested in specifically recruiting smokers for some portions of this study as well as non-smokers for other portions of this study.
- Must weigh a minimum of 110 lbs and no more than 250 lbs unless subject is over 6 feet tall.
- Must have a hemoglobin value greater than or equal to 11 g/dL.
- Baseline heart rate \geq 45 bpm and \leq 85 bpm.
- CO value \leq 2.0% FCOHb (unless we are specifically interested in recruiting smokers)
- Physical status of ASA I or II (American Society of Anesthesiology Class 1; Healthy subjects without any systemic disease at all. American Society of Anesthesiology Class II; subjects with mild systemic disease)
 - The ASA definition strictly applies to the systemic disease portion of the classification
- Blood Pressure (Systolic BP \leq 140 mmHg and Diastolic BP \leq 90 mmHg).
- Able to read and communicate in English
- Has signed written informed consent
- Female, non-pregnant.
- Female subjects will be provided with a pregnancy test free of charge.

Exclusion Criteria (Ineligible subjects)

- Subjects who do not understand the study and the risks involved.
- Subjects with BMI $>$ 35 that a medical professional classifies as morbid obesity or has an increased risk for participation
- Subjects with open wounds, lacerations, inflamed tattoos or piercings, visible healing wounds.
- Subjects with frequent or severe headaches and/or migraine headaches.
- Subject has known drug or alcohol abuse. Subjects who uses recreational drugs.
- Subject has experienced a head injury with loss of consciousness within the last year.
- Any chronic bleeding disorders (i.e. hemophilia)

- Any history of a stroke, myocardial infarction, seizures or heart attack.
- Any cancer or history of cancer (not including skin cancer).
- Chronic neurological diseases (i.e. multiple sclerosis, Huntington's Disease).
- Any cardiac dysrhythmias (i.e. atrial fibrillation)(without physicians clearance)
- Subject has known neurological and/or psychiatric disorder (i.e. schizophrenia, bipolar disorder) that interferes with the subjects' level of consciousness.
- Known or concurrent chronic usage of psychoactive or anticonvulsive drugs. Subjects with psychiatric conditions or are on psychiatric medications (i.e. tricyclic antidepressants, MAO inhibitors, Lithium, neuroleptics, anxiolytics or antipsychotics, except SSRIs).
- Subject has any medical condition which in the judgment of the investigator and/or medical staff, renders them ineligible for participation in this study, such as Reynauds Syndrome.
- Subject has Wolff-Parkinson-White Syndrome or Stokes-Adams Syndrome
- Inability to tolerate sitting still or maintain minimal movement for up to 90 minutes.
- For studies involving finger sensors: subjects with polished, gel or acrylic nails, skin abnormalities affecting the fingers or arms (such as psoriasis, eczema, angioma, scar tissue, burn, fungal infection), distinct finger edema, substantial skin breakdown damaged and/or finger nail deformities (specific finger will not be used, unless we are specifically testing sensors in use with nail polish, gel, and /or acrylic nails).
- Subjects who have/are currently taking anticoagulant medication.
- Subjects who have had caffeine consumption the day of the study.
- Subjects who have taken pain medication within 24 hours of start of study. Unless minimal preventative dose recommended for adults (discretion of physician).
- Subjects having either signs or history of peripheral ischemia.
- Subjects who have had invasive surgery within the past year- including but not limited to major dental surgery, gallbladder, heart, appendix, major fracture repairs (involving plates/ screws), jaw surgery, Urinary tract surgery, plastic surgery, major ENT surgery, joint replacement or gynecological surgeries, heart surgery or thoracic surgery.
- Subjects who have had minor surgery or conditions in the past two months including but not limited to minor foot surgery (bunion), arthroscopic procedure, blood donation, plasma donation, skin biopsy/ procedures, root canal, fractures, eye surgery, and other minor procedures.
- Subjects that have been on antibiotics had congestion, head colds, flu, ear infection, chest congestion will have a 2 week waiting period from the time of finishing medications and must have no more symptoms.
- Subjects with claustrophobia, or anxiety.
- Subjects who have been in severe car accidents or a similar type of accidents will have a 12 month waiting period, from the time of the accident; unless upon further medical history questions the physician determines it does not place the subject in any additional harm, increase their risk, or compromise the subjects' safety.
- Subjects who have had a concussion will have a 12 month waiting period, from the time of the concussion.
- Subjects with chronic unresolved asthma, lung disease or respiratory disease.
- Subjects with allergies to lidocaine, latex, adhesives, or plastic.
- Subjects with heart conditions, Diabetes or hypertension.
- Subjects who have given vaginal delivery will have a 6 month waiting period. Subjects who had a pregnancy terminated, a miscarriage or had a C-section will have a 12 month waiting period.

- Subjects who intend on participating in any heavy lifting, repetitive movement of their wrist (including riding a motorcycle) or exercise (working out, riding a bike, riding a skate board etc.), or any activity that will put additional stress on the wrist within 24 hours following a study involving an arterial blood draw and/or arterial line placement.
- Discretion of investigator/study staff

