13.1.7. Lidocaine (injection) risks

13.1.7.1. Insertion of the Lidocaine may be discomforting and can feel like a slight pinch along with a warm/burning sensation.

13.1.7.2. Other anticipated adverse events that may occur, include but are not limited to:

- Flushing or redness of the skin
- Itching skin
- Small red or purple spots on the skin
- Unusually warm skin
- Bruising
- Bleeding at the application site
- Swelling

These adverse events are expected to be temporary.

Although not common, it is also possible to have an allergic reaction to injectable lidocaine. Subjects should not take part in this study if they are allergic to lidocaine injection or other types of numbing medicine, or if they have a heart rhythm disorder called Wolff-Parkinson-White Syndrome or Stokes-Adams syndrome. Subjects are instructed to tell the study staff right away if they experience hives; difficulty breathing; swelling of your face, lips, tongue or throat.

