13.1.8. Ethyl Chloride (Lidocaine Spray)

13.1.8.1. Ethyl Chloride is a topical anesthetic which is used to prevent pain by cooling the skin.

13.1.8.2. Although unlikely, the anticipated adverse events that may occur, include but are not limited to:

- 13.1.8.2.1. Changes in skin color (ie. Flushing or redness of the skin)
- 13.1.8.2.2. Delayed wound healing
- 13.1.8.2.3. Rash
- 13.1.8.2.4. Itching
- 13.1.8.2.5. Swelling

These adverse events are expected to be temporary.

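### Section 13.1.7.2 bars volunteers allergic to numbing medicines other than lidocaine, but the section 9 exclusion list used for screening does not name them

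*Protocol*

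**What the plan says.** Three parts of the protocol bear on this point.

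- **Risk text.** Section 13.1.7.2, under the lidocaine injection risks, says: "Subjects should not take part in this study if they are allergic to lidocaine injection or other types of numbing medicine". The same sentence also bars people with Wolff-Parkinson-White or Stokes-Adams syndrome.
- **Eligibility list.** The exclusion criteria in section 9 contain the allergy item "Subjects with allergies to lidocaine, latex, adhesives, or plastic" and, separately, "Subject has Wolff-Parkinson-White Syndrome or Stokes-Adams Syndrome". They also contain a judgment-based item, "Subject has any medical condition which in the judgment of the investigator and/or medical staff, renders them ineligible for participation in this study", and close with a general discretion item.
- **Use of the list.** Section 6.2.4 says: "Subjects who do not meet the inclusion and exclusion criteria will not be eligible to participate in the study". Section 6.1.2 has the phone screener qualify callers on the same criteria.

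On the numbing agents themselves, 5.2 lists lidocaine and, as a separate item, "Ethyl Chloride/Pain Ease". Section 13.1.8 is headed "Ethyl Chloride (Lidocaine Spray)" and explains: "Ethyl Chloride is a topical anesthetic which is used to prevent pain by cooling the skin". The risk list in 13.1.1 also speaks of a lidocaine spray.

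**The concern.** The protocol gives a flat bar in its risk section and a narrower one, as far as numbing medicines go, in the list that screeners are told to work from. A bar that appears only in the risk section can be missed by someone working through section 9 item by item.

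What is at stake is subject safety and consistent enrolment. These are healthy volunteers, and section 15 offers them no personal benefit. Section 13.1.7.2 itself treats allergic reaction to injected lidocaine as uncommon but possible, and tells subjects to report hives, breathing difficulty or swelling at once. Two staff members faced with the same volunteer could reach different decisions, depending on which section each had in mind. No endpoint, sample size or analysis depends on this.

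**Working it through.** No arithmetic applies, so the check sets the texts side by side.

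**Step 1: match each bar in the 13.1.7.2 sentence to a named exclusion in section 9.**

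| Bar in 13.1.7.2 | Named in section 9? |
|---|---|
| Allergy to lidocaine injection | Yes, in the allergy item |
| Allergy to other types of numbing medicine | No |
| Wolff-Parkinson-White syndrome | Yes, in its own item |
| Stokes-Adams syndrome | Yes, in the same item |

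Three of the four bars are carried over and one is not. The section 9 allergy item is narrower only for numbing medicines. It also covers latex, adhesives and plastic, which 13.1.7.2 does not mention.

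**Step 2: ask whether redaction explains the gap.** The blacked-out lines in section 9 stand before the inclusion criteria. The exclusion list shows none, and the allergy item is a complete sentence. The gap does not look like an effect of redaction.

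**Step 3: ask which text screeners apply.** Sections 6.1.2 and 6.2.4 both point to the inclusion and exclusion criteria, and 10.3 likewise refers to a set of qualifying criteria. None of them points to the risk text in section 13.

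**Step 4: follow one volunteer through.** Take someone with a known allergy to a numbing medicine, but not to lidocaine, latex, adhesives or plastic, who meets all other criteria. No named exclusion applies. Two routes could still keep this person out: the discretionary items in section 9 (repeated in 10.3), which permit exclusion without requiring it, or staff applying 13.1.7.2 directly.

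**Step 5: check the numbing agents.** Section 5.2 lists ethyl chloride/Pain Ease apart from lidocaine, while 13.1.1 and 13.1.8 attach a lidocaine label to the spray. Section 13.1.8 describes an agent that acts by cooling the skin. The naming is inconsistent, but 13.1.8 states no allergy bar for ethyl chloride, so the absence of ethyl chloride from the allergy item is not in itself a contradiction.

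**The case against.** The strongest reply is that the protocol must be read as a whole. Its opening page commits the study to everything the protocol stipulates, and 13.1.7.2 is part of it. Read cumulatively, the two passages already keep this volunteer out. Section 6.2.4 makes people who fail the criteria ineligible; it does not say that everyone who clears the named items must be enrolled. The exclusion list is also open-ended because of its discretionary items.

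Much of this stands. A reader might infer that section 9 admits the person whom 13.1.7.2 bars. The documents do not support that: section 9 is silent on this person. What remains is that the bar is absent from the list screeners use. Discretion does not fully answer this, because the two syndromes in the same sentence were listed by name although the same discretion covered them.

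A second reply is that the question may be asked elsewhere. The Health Questionnaire is not among the documents, 6.2.6 requires a medical history, and the visible numbering runs from 6.2.11 to 6.3.5, so some steps before the arterial line is placed cannot be seen. This stands as a limit: nobody can say from these documents that the question goes unasked. But even if it is asked, a positive answer would match no named exclusion.

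A third reply is that a physician certified in advanced cardiac life support is present throughout. That bears on the response to a reaction, not on who is enrolled.

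**Conclusion.** The inconsistency is real and limited. One of the four bars in the 13.1.7.2 sentence, allergy to numbing medicines other than lidocaine, has no named counterpart in section 9. Such a volunteer would be kept out only by staff discretion or by staff applying the risk text. Because the other three bars were carried over, an oversight is the natural explanation, but that is an inference and the documents do not say so.

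The conclusion rests on two assumptions: that the exclusion list shown is complete, which the absence of redaction there supports, and that screeners work from section 9, as 6.1.2 and 6.2.4 say. The documents give no prevalence of such allergies, so the number of volunteers concerned cannot be estimated.

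A reader might also infer that ethyl chloride allergy is wrongly left out of section 9, or that the spray label would mislead screeners in a particular direction. Neither is supported. No passage names an allergy bar specific to ethyl chloride, and a screener who took lidocaine to include the spray might just as well extend the exclusion to it. The label is a separate, minor inconsistency.

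The point is worth correcting because it concerns subject safety and is cheap to settle. Which wording is right is for the sponsor's medical staff and the IRB to decide.

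**What to change.** The sponsor's medical staff should reconcile the numbing-medicine part of the section 9 allergy item with 13.1.7.2, so that both state the same rule, and then confirm that the Health Questionnaire matches it. Only that part needs aligning. Latex, adhesives and plastic have no place in a paragraph on lidocaine risks, so the two lists need not be identical.

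As a minor accompanying edit, reconcile the spray label in 13.1.1 and 13.1.8 with 5.2, which lists ethyl chloride/Pain Ease separately from lidocaine.

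The cost is a wording amendment, which 18.1 sends to the IRB before use, a check of the questionnaire, and possibly a few more exclusions at screening, a number the documents do not give. No change to the statistical analysis is needed.
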